2.3 Data Conventions

2.3.1 Study day

For each subject, the reference start date (also referred to as Day 1) is the date when the subject had an energy-based therapy. Study day will be calculated using visit date and the

reference start date as follows: (1) study day = visit date – reference start date + 1, for any visit date \geq reference start date. (2) study day = visit date – reference start date, for any visit date < reference start date.

2.3.2 Imputation for missing measurement or assessment data

On some certain parameters, a subject has multiple assessments prior to the initiation of the energy-based therapy at Day 1. Specifically, those parameters include vital sign measurements, urine pregnancy tests, Clinician's Telangiectasia Assessments (CTA), Satisfaction assessments for Rosacea facial redness, FACE-Q satisfaction with skin scale. The baseline values for subjects on those parameters will be derived using the rule of Last Observation Carried Forward (LOCF) as follows: The value immediately prior to the initiation of energy-based therapy at Day 1 will be used as the baseline value; if that value is missing or does not exist, then the value at screening will be used. On other parameters, a subject has one single assessment or measurement during screening or prior to the initiation of the energy-based therapy at Day 1, then the single value will simply be used as the baseline value for the subject.

There is no imputation of missing values for any post-baseline measurements or assessments. All data summaries and analyses of post-baseline data will be conducted using observed cases.

2.3.3 Study end date for patient

Study end date for each individual patient is defined as the date of completion of last assessment on the Day 56 visit or the date of the early withdrawal visit in case of earlier discontinuation from treatment. Note that subjects who are discontinued earlier from treatment for whatever reasons will be invited to attend the early withdrawal visit for the end-of-study data collection.

2.3.4 Study completer

Study completers are defined as those evaluable subjects who have completed the last assessment on the Day 56 visit.

2.3.5 Other conventions

Summary statistics (used interchangeably with the term descriptive statistics) for continuous data include sample size (N), mean, standard deviation (SD), median, minimum, and maximum. Categorical variables will be summarized using sample size (N), frequency and percentages of patients. In calculating the percentage, unless specified otherwise, the count of

subjects "at risk" will be used as denominator. Ordinal variables will be handled as categorical variables when presenting summary statistics using ordinal variables.

Change from baseline is calculated as follow-up minus baseline. Percentage change from baseline is calculated as change from baseline divided by baseline value, then multiplied by 100. If baseline value is zero, percentage change from baseline will be undefined. If baseline value is missing, percentage change from baseline will be missing.

Data will be pooled across clinical sites/centers for analyses with an exception of one patient enrollment table.

The International System of Units (Système international d'unités or SI) is the current international standard metric system. The SI units will be used for the reporting in all Tables/Figures/Listings for this study.

All statistical analysis and reporting will be performed using SAS[®] version 9.3 or higher.

3. Disposition and Exit Status

3.1 Screening Log Data

Subject eligibility criteria (including both inclusion and exclusion criteria) and date of informed consent will be listed for the enrolled population. Note that date of informed consent will be included in the subject disposition listing.

3.2 Disposition and Exit Status

Reasons for exclusion from safety population will summarized and will be listed for the enrolled population. Subject disposition will be listed for the enrolled population.

4. Demographics and Baseline Characteristics

4.1 Demographics

All patient demographic and baseline characteristic data will be summarized using descriptive statistics for the enrolled population and the safety population.

Age (years) captured at enrollment will be summarized as a continuous variable. Other continuous variables to be presented include weight, height and body mass index (BMI) and baseline vital signs (i.e., blood pressure, pulse rate, and oral body temperature). Categorical or ordinal variables to be presented include sex, race, ethnicity, the type of energy-based therapy on Day 1 and Fitzpatrick skin phototype.

Demographic tables will also be presented for the safety population stratified by the presence or absence of Treatment-Emergent Adverse Events (TEAE) during the study, and by whether having had at least 1-grade worsening from baseline in Clinician's Telangiectasia Assessments (CTA) at any timepoint in the study.

All demographic data will be listed.

4.2 **Prior Medications**

Prior medications are defined as any medication which is administered any time prior to the initiation of the energy-based therapy treatment at Day 1 regardless when the medication stops.

Prior medications will be coded by the Anatomical Therapeutic Chemical (ATC) classification system according to the World Health Organization (WHO) Drug WHODDE March 2016 or later. Medications will be summarized by ATC class (level 2) and subclass preferred term (PT) for all patients in the safety analysis cohort.

The summary tables will show the frequency count and percentage of patients with at least 1 usage of medications on the subclass level within each ATC class, sorted alphabetically. Percentages will be calculated using the number of patients in the safety population as the denominator.

All prior medications will be listed.

4.3 Concomitant Medications

Concomitant medications encompass any medication that is administered any time after the initiation of the energy-based therapy, regardless of when the medication starts or stops. Note that concomitant medication includes on-going prior medications. i.e., medicinal products

that are administered prior to the initiation of the energy-based therapy at Day 1 and is still being used during the study.

Any concomitant medication will be recorded at each visit, including the medication name, dose, unit, frequency, route of administration, indication, and medication start and end dates.

Concomitant medications will be coded by the ATC classification system according to the WHO Drug WHODDE March 2016 or later. Medications will be summarized by ATC class (level 2) and subclass (PT) for all patients in the safety analysis cohort.

The summary tables will show the frequency count and percentage of patients with at least 1 usage of medication on the subclass level within each ATC class, sorted alphabetically. Percentages will be calculated using the number of patients in the safety population as the denominator.

All concomitant medications will be listed.

Prohibited Medications are listed in Section 5.6.10.1 of the Protocol. Prohibited concomitant medications that were inadvertently administered will be summarized similarly as that for concomitant medications. Listing will also be provided for prohibited medications that were inadvertently administered.

Per Section 5.6.10.2 of the Protocol, treatments by laser, light-source, or other energy based therapies to the face, other than those treatments performed as part of the study, are not permitted during the study. Dermatological treatments on the face (e.g., facial peels, microdermabrasion, exfoliating treatments) are prohibited for the duration of the study. The use of any of such treatments is considered as a deviation (violation) of protocol per this SAP. Listing of protocol deviation (violation) will be provided.

4.4 Medical History

Descriptions of medical history findings will be coded using Medical Dictionary for Regulatory Activities (MedDRA) version 20.1 or later. Medical history will be summarized for the safety population by the number and percentage of patients within each system organ class (SOC) and PT, sorted descending overall frequency. Medical history will be listed for all patients in the safety population. Medical history data listings will be sorted by patient number, start date, SOC, PT and verbatim term.

5. Efficacy Analyses

For this study, efficacy analyses will be exploratory in nature. Certain efficacy analyses will be conducted to evaluate the effect of daily application of oxymetazoline 1.0% cream adjunctive to energy-based therapy on Clinician Erythema Assessment (CEA), rosacea facial redness and subject's satisfaction rating. These analyses as described below will be based on the evaluable population.

5.1 Collection of Efficacy Measurements and Derivation of Efficacy Variables

The following measurements and variables are of the primary interest.

- Measurement: CEA; Variable: Improvement on CEA from baseline. An improvement is defined by a negative change from baseline.
- Measurement: Satisfaction rating per the Satisfaction Assessment for Rosacea Facial Redness;
 Variable: Proportion of subjects who rate "Satisfied" or "Very Satisfied".
- Measurement: Satisfaction rating per the FACE-Q Satisfaction with Skin Scale; Variable: Proportion of subjects who rate "Somewhat Satisfied" or "Very Satisfied".
- Measurement: Rosacea facial redness using DIA of standardized facial photographs; Variable: Percentage change from baseline in rosacea facial redness.

5.2 Analyses of Efficacy Variable(s)

There is no statistical testing of hypotheses pertaining to efficacy variables. Statistical inference will be limited to the construction of distribution-free 95% CI for the median percentage change from baseline variables, since these percentage change variables are known for the deviation from normality in distribution. The distribution-free 95% CI for the

median will be calculated using SAS[®] procedure Proc Univariate. In this section, summary tables mainly in the forms of descriptive statistics will be presented for the above-specified efficacy and patient reported outcomes (PRO) variables.

- The number and percentage of subjects with at least a 1-grade improvement on the CEA from baseline, by visit/timepoint.
- Summary statistics of CEA by visit/timepoint.
- Proportion of subjects indicating Satisfied or Very Satisfied with treatment on the Items of Satisfaction Assessment for Rosacea Facial Redness, by visit. There are two items (questions). See Appendix 14.2 of the Protocol. Item 1 (Question 1) is: Right now, how satisfied are you with the appearance of your facial redness? Item 2 (Question 2) is: Right now, how satisfied are you with the appearance of the amount of redness on your face? This summary will be repeated for each of the two items.
- Proportion of subjects indicating Somewhat Satisfied or Very Satisfied with treatment on the FACE-Q Satisfaction with Skin Scale, by visit. There are 12 questions on the FACE-Q Satisfaction assessments regarding the subjects' rating of their satisfaction with skin. See Appendix 14.3 of the Protocol. This summary will be repeated for the response to each of the 12 questions, and for the average response to the 12 questions.
- Percentage change from baseline in rosacea facial redness using Digital Image Analysis (DIA) of standardized facial photographs, by visit/timepoint. This summary table will be presented if the rosacea facial redness data are obtained and such facial redness can be quantified. This summary table for the percentage change from baseline in rosacea facial redness will be provided.

5.3 Other Analyses of Efficacy Variable(s)

Not applicable.

5.4 Subgroup Analyses for Efficacy Variables

Not applicable.

6. Safety Analyses

All safety analyses will be based on the safety population. Safety will be assessed primarily in terms of the frequency count and the binominal incidence proportion of the adverse events of interest. The binomial incidence proportion for a given event of interest during a certain period is defined as the number of unique patients who have experienced the event of interest in the period divided by the number of patients in the safety population, then multiplied by 100. Note that, for the calculation of the incidence proportion, the numerator is counted at subject level. Specifically, if a subject has experienced the event(s) of interest (at a given summarization level) more than once during the period, he/she is counted only once into the numerator. The binomial incidence proportion of an event is also called the percentage of subjects who have had such an event. The two terms are used interchangeably. The 95% CIs for binomial incidence proportion will also be calculated using the Clopper and Pearson exact method (via SAS[®] procedure Proc Freq).

6.1 Exposure to Study Treatment(s)

Treatment duration in days will be calculated as: Date of last dose of study medication -Date of the initiation of the energy-based therapy + 1. Treatment duration will be summarized using descriptive statistics. Number of energy-based therapies administered and number of days in which Oxymetazoline 1.0% cream had been applied over the study period will be summarized using descriptive statistics.

Partial or missing start/end dates will be handled as per Section 2.3.3.

All treatment data will be listed.

6.2 Adverse Events

Adverse events will be coded using MedDRA version 20.1 or later to give a PT and a SOC term for each event.

An adverse event (AE) is defined as any untoward medical occurrence in a clinical investigational patient administered a pharmaceutical (investigational) product and which does not necessarily have to have a causal relationship with this treatment.

All AEs will be included in by-subject AE listings. A separate listing will be created with all the distinct levels of SOC and PT, and the verbatim investigator description reported in the study. Sorting will be by earliest observed SOC, PT within SOC and then verbatim description.

A treatment-emergent adverse event (TEAE) is a post-baseline AE where (i) there is no pretreatment AE of the same MedDRA primary SOC and PT; or (ii) the maximum severity during the post-baseline period is greater than the maximal severity of any pre-treatment AE of the same MedDRA primary SOC and PT during the screening/baseline period. Note that the post-baseline period of the study starts upon the initiation of the energy-based therapy at Day 1.

Any AEs reported after signing of the Informed Consent Form and prior to the energy-based therapy on Day 1 are considered pretreatment AEs (PTAEs)

Relationship to study drug is categorized as 'related', 'possibly related', 'unlikely related', 'not related', and 'not assessable'. Relationship to trial medication as per investigator is not expected to be missing after data cleaning. However, if relationship is confirmed as missing, the AE will be considered as treatment related as per PI.

An overall summary of frequency count and the binomial incidence proportion with associated 95% CIs will be presented to describe the incidents of TEAEs. Note that 95% CIs of the binomial incidence proportion will be presented for the overall summary analyses of TEAEs, but not for the by-visit/timepoint analyses. Percentages and corresponding 95% CIs will be displayed to 1 decimal place.

Each type of AE will be tabulated by SOC and PT within SOC. The SOC and PT within SOC will be sorted by descending frequency. If a subject has multiple occurrences (start and stop) of an event associated with a specific SOC and PT, a patient will only be counted once in the incidence count for the SOC level and once at each PT within the SOC level.

The incidence of all TEAEs by SOC and PT will be presented for the following categories:

• Any TEAE

• Any TEAE related to energy-based therapy and leading to discontinuation of study medication

• Any TEAE related to treatment (i.e., study medication or energy-based therapy or both)

- Any TEAE by maximum severity
- Any PTAE

The following listings will be provided:

- Listing of all TEAE
- Listing of patients with TEAEs related to energy-based therapy and leading to discontinuation of study medication
- Listing of patients with TEAEs leading to discontinuation of treatment

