### 5 STUDY ENDPOINTS

### 5.1 Primary Endpoints

The primary endpoints of the study are:

- The incidence of treatment emergent adverse events (TEAEs) and serious adverse events (SAEs).
- The number and percent of subjects with at least a 1-grade worsening from baseline in the Dermal Tolerability Assessment at any timepoint over the treatment period.
- The number and percentage of subjects with at least a 1-grade worsening from baseline in the CTA at any timepoint over the treatment period.

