## 7.1.2.1 Adverse Events

# **Adverse Event Definition**

An AE is defined as any untoward medical occurrence in a clinical study subject administered a medicinal product that does not necessarily have a causal relationship with this treatment. An AE can therefore be any unfavorable and unintended sign (including an abnormal laboratory finding), symptom, or disease temporally associated with the use of a medicinal (investigational) product, whether or not it is related to the medicinal (investigational) product. This includes an exacerbation of pre-existing conditions or events, intercurrent illnesses, drug interaction or the significant worsening of the indication under investigation that is not recorded elsewhere in the eCRF under specific efficacy assessments. Anticipated fluctuations of pre-existing conditions, including the disease under study, that do not represent a clinically significant exacerbation or worsening need not be considered AEs.

Adverse event collection will commence from the time the subject signs the ICF. It is the responsibility of the investigator to document all AEs that occur during the study. AEs will be elicited by asking the subject a nonleading question, for example, "Have you experienced any new or changed symptoms since we last asked/since your last visit?" Adverse events should be reported on the appropriate page of the eCRF.

A TEAE is any event not present prior to the initiation of the study treatments or any event already present that worsens in either intensity of frequency following exposure to the study treatments. Any AEs reported after signing the ICF and prior to study treatment are considered pretreatment AEs (PTAEs).

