The purpose of this statistical analysis plan (SAP) is to provide details of the statistical analyses and reporting that are outlined in the study protocol, which is dated on Oct 12, 2017 and titled "Multicenter, Open-Label, Interventional Study on the Safety and Tolerability of Oxymetazoline and Energy-Based Therapy in Subjects with Rosacea". This SAP should be reviewed in conjunction with the study protocol. Information contained in the protocol will not be restated unless it is essential for the descriptions in this SAP. In case of any discrepancies (for example, the definition of the Safety Analysis Population) between the protocol and the SAP, the SAP will supersede the protocol, as the SAP is intended to be more specific and precise with respect to statistical analysis and reporting. Any amendments to the SAP will be made prior to database lock. Any additional analyses not described in the final SAP or deviations from the final SAP will be documented in the clinical study report.

This study is a Phase 4 study sponsored by Allergan Plc. This study is a multicenter, interventional, open-label safety and tolerability study to evaluate the safety and tolerability of oxymetazoline HCl cream 1.0% when used as an adjunctive treatment to energy-based therapy for subjects with moderate to severe persistent facial erythema associated with rosacea.

Approximately 45 subjects will be enrolled into this study at 4 clinical sites in the United States. The duration of the study for each subject is 10 weeks. This includes a screening period of up to 2 weeks, a treatment period of 8 weeks, comprising of daily dosing of study drug and 2 energy-based therapy sessions, followed by a final exit visit at Week 8 (Day 56).

There will be no interim analysis. One final analysis is planned for this study. The final analysis will be performed at the completion of the study. Database lock will be executed for the final analysis.

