6.3 Serious Adverse Events

A serious adverse event (SAE) is any AE occurring at any dose that results in any of the following outcomes: death, a life-threatening AE, inpatient hospitalization or prolongation of existing hospitalization, a persistent or significant disability/incapacity, or a congenital anomaly/birth defect. Important medical events that may not result in death, be life-threatening, or require hospitalization may be considered a SAE when, based upon appropriate medical judgment, they may jeopardize the patient and may require medical or surgical intervention to prevent one of the outcomes listed in this definition. Allergan considers all cancer AEs as SAEs. In addition, an abortion (spontaneous or non-spontaneous) is also considered a SAE. Any pre-planned surgery or procedure should be clearly documented in the source documents at the center by the medically qualified investigator at the time of the patient's entry into the study. If it has not been documented at the time of the patient's entry into the study, then it should be documented as a SAE and reported to Allergan.

If an unexpected AE is serious and suspected, it is a suspected "unexpected" serious adverse reactions (SUSAR). See Section of 7.1.2.1.2 of the Protocol for details, such as what is considered as "unexpected".

An overall summary of frequency count and the binomial incidence proportion with the associated 95% CIs will be presented to describe the incidents of treatment emergent SAEs. Note that 95% CIs of the binomial incidence proportion will be presented for the overall summary analyses of SAE, but not for the by-visit/timepoint analyses. Percentages and corresponding 95% CIs will be displayed to 1 decimal place.

The incidence of all treatment-emergent SAEs by SOC and PT within SOC will be presented for the following categories:

- Any SAE
- Any SAE related to energy-based therapy and leading to discontinuation of study

medication

- Any SAE related to treatment (i.e., study medication or energy-based therapy or both)
- Any SAE by maximum severity
- Any SUSAR

The following listings will be provided:

- Listing of subjects who died
- Listing of subjects with treatment-emergent SAEs
- Listing of subjects with treatment-emergent SAEs related to energy-based therapy and leading to discontinuation of study medication
- Listing of patients with treatment-emergent SAEs leading to discontinuation of

treatment

• Listing of patients with any SUSAR

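### SAP 6.2 defines a treatment-emergent event more narrowly than the protocol, does not declare it, and carries the narrower rule into the SAE tables

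*SAP*

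**What the plan says.** Protocol 7.1.2.1 (Adverse Event Definition) gives two routes to treatment emergence. The first is a new event: "A TEAE is any event not present prior to the initiation of the study treatments". The second is "any event already present that worsens in either intensity of frequency following exposure to the study treatments", where the word before frequency is evidently a slip for or.

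SAP 6.2 also gives two routes, but both are keyed to the coded term. A post-baseline event counts if "there is no pretreatment AE of the same MedDRA primary SOC and PT", or if "the maximum severity during the post-baseline period is greater than the maximal severity of any pre-treatment AE of the same MedDRA primary SOC" and preferred term (PT) in the screening and baseline period. Post-baseline starts with the energy-based session on Day 1. Pretreatment events are those reported from consent up to that session.

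SAP 6.3 builds on this rule. The overall SAE count and incidence "will be presented to describe the incidents of treatment emergent SAEs". The breakdown by SOC and PT and the listing of subjects with SAEs are restricted in the same way.

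Protocol 5.1 makes the incidence of TEAEs and SAEs the first primary endpoint. The SAP introduction states that where the two documents differ "the SAP will supersede the protocol, as the SAP is intended to be more specific and precise". SAP section 11 declares two departures from the protocol: the replaced modified intent-to-treat population and the added per-protocol population. The TEAE definition is not mentioned.

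**The concern.** Two definitions of the first primary endpoint are in force, and the narrower one governs without being declared. Three kinds of post-treatment event are affected when the subject already has a pretreatment AE of the same SOC and PT:

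- **More frequent, same grade.** The protocol counts it and the SAP does not. This is a clear contradiction.
- **Resolved, then a new episode at the same or a lower grade.** The SAP excludes it. The protocol wording is open to reading here.
- **Becomes serious without a higher severity grade.** It is not treatment-emergent under the SAP, so it falls outside the SAE tables and the SAE listing.

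The study has a single arm, so no comparator suffers the same loss, and each incidence is read on its own. The rule also takes no account of causality. An excluded event that the investigator judged related leaves the treatment-related TEAE table as well, and one that led to stopping treatment leaves the corresponding TEAE listing.

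**Working it through.** **1. The two rules applied to the same histories**

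| Course in one subject, same SOC and PT | Protocol 7.1.2.1 | SAP 6.2 / 6.3 |
|---|---|---|
| A. No pretreatment AE; event after Day 1 session | TEAE | TEAE |
| B. Mild before; mild and moderate after | TEAE | TEAE (maximum severity rises) |
| C. Mild before and ongoing; more often, still mild, after | TEAE (frequency) | Not a TEAE |
| D. Mild or moderate before, resolved; new mild episode after | Open to reading | Not a TEAE |
| E. Pretreatment AE; becomes serious after, grade not higher | SAEs are named in the primary endpoint | Outside SAE tables and SAE listing |
| F. Condition known before consent, in medical history only; reported after Day 1, unchanged | Already present, so not a TEAE | TEAE (no pretreatment AE recorded) |

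Row E can occur because the protocol grades severity by interference with everyday activities, defines seriousness by outcomes such as hospitalization, and records the two as separate items.

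**2. Direction**

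For a term that the subject had recorded as a pretreatment AE (rows B to E), every event that passes the SAP rule shows a rise in severity, which is also worsening in intensity under the protocol. The SAP can therefore remove such a subject from a numerator but cannot add one. Row F runs the other way, so the direction is not fixed for the trial as a whole.

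**3. Denominator**

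The documents state no figure for this rule. The sample size in Protocol 8.2 supplies the denominator, and it reproduces with p0 = 0.082, δ = 0.14, pu = p0 + δ = 0.222, one-sided 5% and 80% power:

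n = [(z0.95·√(pu(1−pu)) + z0.80·√(p0(1−p0)))/δ]² = 42.67, rounded up to 43, with about 45 enrolled.

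The TEAE definition does not enter this formula, so the sample size is unaffected.

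**4. Effect of one subject**

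- 1/45 = 2.2 points (1/43 = 2.3 points).
- At the protocol's 8.2% treatment-related rate, 45 × 0.082 = 3.7 subjects are expected. For scale, 4/45 = 8.9% (exact 95% CI 2.5% to 21.2%) and 3/45 = 6.7% (1.4% to 18.3%).
- For SAEs (Clopper-Pearson, the SAP's method), 1/45 = 2.2% has lower limit 1 − 0.975^(1/45) = 0.06%, shown as 0.1%, and upper limit 11.8%. For 0/45 the upper limit is 1 − 0.025^(1/45) = 7.9%.

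**5. How many subjects**

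This cannot be computed from the documents. Let q be the share of subjects with a pretreatment AE and r the share of those with the same PT afterwards at no greater severity. Both are assumptions. The expected number affected is 45·q·r, and the chance of at least one is 1 − (1 − qr)^45.

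| q | r | Expected subjects | Points | Chance of at least one |
|---|---|---|---|---|
| 2% | 10% | 0.09 | 0.2 | 8.6% |
| 5% | 25% | 0.56 | 1.25 | 43.2% |
| 10% | 25% | 1.12 | 2.5 | 68.0% |
| 20% | 50% | 4.5 | 10.0 | 99.1% |

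These are losses at PT level. The loss for any TEAE is smaller, because a subject with another TEAE still counts. The last row needs one subject in five to report an AE in a window that runs from zero days (screening and baseline may share a day) to about 14.

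**The case against.** The case for leaving the rule alone has real weight.

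- **Short trigger.** Only AEs recorded between consent and the Day 1 session count against a later event; medical history does not. Zero affected subjects is possible.
- **Nothing leaves the data.** All AEs stay in the by-subject listings, and deaths have their own listing. The fault is misclassification in summary outputs.
- **Remote SAE case.** It needs the same term before Day 1 at an equal or higher grade, followed by seriousness. A change in severity must be recorded as a separate event, so a rise in grade is caught.
- **No decision turns on it.** The SAP sets no safety test or threshold, and the intervals for 3/45 and 4/45 overlap almost entirely.
- **Version.** The SAP cites the protocol of Oct 12, 2017; the one supplied is Version 2 of 06 Feb 2018. Whether the definition differed in the cited version cannot be checked.

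These points limit the size and leave the conflict in place. The supersession clause settles which rule governs, but it does not replace a declaration in section 11.

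Three stronger readings are tempting and are not supported:

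- **The SAP rule can only lower incidence and so always favours tolerability.** Row F shows the opposite effect. It is limited because the protocol does not require anticipated fluctuations of pre-existing conditions to be recorded as AEs.
- **Recurrent local reactions are the main loss.** The drug's local reactions described in Protocol 4.3 are largely application-site terms, which should not arise before any study drug is applied. Dryness, scaling, stinging/burning, pruritus and telangiectasia are also analysed by grade change from baseline, outside the TEAE rule.
- **A definite number of subjects is lost.** No count has a basis in the documents.

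**Conclusion.** The concern holds: SAP 6.2 is wrong as written. It drops the protocol's frequency criterion, excludes same-grade or lower-grade recurrences on which the protocol is unclear, and through SAP 6.3 can keep a post-treatment serious event out of the SAE tables and listing. All of this bears on the first primary endpoint and is undeclared.

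The weight is minor to moderate, and the point is not a must-fix. One affected subject is worth 2.2 points, or the difference between reporting one SAE and none. The number affected is probably small and may be zero. That judgement rests on the short pretreatment window, since the documents give no pretreatment AE or recurrence rate. The one-directional effect applies only to terms that the subject had recorded as a pretreatment AE.

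**What to change.** - **SAP 6.2.** Count as treatment-emergent any AE with onset on or after the first energy-based session, plus any AE ongoing at that session that then worsens in intensity or frequency. The AE data items in the protocol include no frequency field, so state that frequency is derived from recorded episodes and their dates, and that each episode is entered separately.
- **SAP 6.3.** Tabulate and list every SAE with onset, or first meeting a seriousness criterion, after the first session, regardless of pretreatment PT history. The listed AE items date only first occurrence and resolution, so state where the date of becoming serious is taken from.
- **SAP section 11.** Record the change. The onset-date rule and the seriousness rule clarify the protocol definition and are not its wording, so they should be described as additions.

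The cost is an SAP amendment before database lock, a modest programming change and a convention for frequency. Reported TEAE and SAE incidence may be slightly higher. Sample size and visit schedule do not change.
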